#### **7.12.6.5 The mean change from Baseline (D1) to Week 2, Week 4, Week 8, and Week 12 in the mean NPRS worst pain score in the affected leg.**

This will be analyzed and presented using the same MMRM model described in the primary analysis but the response variable will be change from baseline in mean weekly worst NPRS score. Baseline NPRS score is the mean of at least 5 days and no more than 7 days of scores from the Screening visit until treatment randomization (D1).

[REDACTED]

The mean weekly NPRS score will be calculated for each subject for each week up to Week 12. Change from baseline in mean weekly NPRS score will be calculated by subtracting the baseline value from the weekly score. Mean change from baseline for the first 4 weeks (with overall average) will be analyzed and presented by the treatment received for the first injection (SP-102, Placebo). Mean change from baseline for the first 12 weeks (Weeks 2, 4, 8, and 12) will be analyzed and summarized by treatment received for second injection (SP-102/SP-102, PBO/SP-102, SP-102/none, PBO/none). As part of this analysis, comparisons will test the mean LS mean differences between the following groups:

- SP-102/none vs. PBO/none

- SP-102/SP-102 vs. PBO/none
- SP-102/none vs. PBO/SP-102
- SP-102/SP-102 vs. PBO/SP-102

NPRS worst pain score is also collected at visits after Week 12 (Weeks 16, 20, and 24), but this score is only collected once, that is, during the clinic visits. This data will not be included in the model but will be included in the summary table.

#### **7.12.6.6 The mean change from Baseline (D1) to Week 2, Week 4, Week 8, and Week 12 in the mean NPRS current pain score in the affected leg**

The current pain intensity “pain now” is measured at every clinic visit and used for assessment of accuracy of pain reporting and monitoring of outlier values. This endpoint will be analyzed and presented using the same MMRM model described in the primary analysis but the response variable will be change from baseline in mean NPRS current pain score at Weeks 2, 4, 8, and 12; with baseline NPRS score as the last score collected prior to the first injection on D1. Mean change from baseline to Week 2 and Week 4 will be analyzed and presented by the treatment received for the first injection (SP-102, Placebo). Mean change from baseline for the first 12 weeks (Weeks 2, 4, 8, and 12) will be analyzed and summarized by treatment received for second injection (SP-102/SP-102, PBO/SP-102, SP-102/none, PBO/none). As part of this analysis, comparisons will test the mean LS mean differences between the following groups:

- SP-102/none vs. PBO/none
- SP-102/SP-102 vs. PBO/none
- SP-102/none vs. PBO/SP-102
- SP-102/SP-102 vs. PBO/SP-102

NPRS average scores are also collected at visits (Weeks 16, 20, and 24) after visit 12. This data will not be included in the model but will be included in the summary table.

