3.5.6.1 Numeric Pain Rating Scale

The NPRS (Appendix E) is an 11-point scale (0 to 10-point scale where 0 is no pain and 10 is worst pain imaginable) that allows the subject to rate the severity of their pain intensity at various points in time (Turk-2003). Twice daily in the morning and evening (approximately 12 hours apart), the subject will use the NPRS to record their average and worst pain in the past 12 hours.

After the Screening Visit, the NPRS will be collected twice daily using the eDiary through W12; thereafter, the NPRS will be collected at clinic visits only. The eDiary

subject assignment should remain the same throughout the trial, and eDiaries should only be re-assigned for completed/withdrawn subjects. The current pain intensity “pain now” will be measured at every clinic visit and used for assessment of accuracy of pain reporting and monitoring of outlier values. Morning and afternoon pain measurements will be investigated for predictability of response.

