#### **7.12.6.4 The mean change from Baseline (D1) to Week 2, Week 4, Week 8, and Week 12 in the mean NPRS average pain score in the affected leg.**

Baseline and post-baseline values for this endpoint is obtained as discussed in [Section 7.12.1](#). A similar approach in modeling the restricted maximum likelihood (REML)-based MMRM as in the primary analysis will be applied for this endpoint. Mean change from baseline to Week 2 and Week 4 will be analyzed and presented by the treatment received for the first injection (SP-102, Placebo). Mean change from baseline for the first 12 weeks (Weeks 2, 4, 8, and 12) will utilize similar MMRM model except that the outcome variable will be change from baseline in mean weekly NPRS average pain score in the affected leg at Weeks 2, 4, 8, and 12, and the fixed effects are as follows: treatment (four groups: SP-102/SP-102, PBO/SP-102, SP-102/none, PBO/none ), week (2, 4, 8, 12), site, Pain Catastrophizing Scale group (<30 or ≥30), baseline averaged daily leg

pain score, and the treatment-by-week interaction. Mean change from baseline for Weeks 2, 4, 8, and 12 will be summarized by treatment received for second injection (SP-102/SP-102, PBO/SP-102, SP-102/none, PBO/none).

As part of this analysis, comparisons will test the mean LS mean differences between the following groups:

- SP-102/none vs. PBO/none
- SP-102/SP-102 vs. PBO/none
- SP-102/none vs. PBO/SP-102
- SP-102/SP-102 vs. PBO/SP-102

NPRS average scores are also collected at visits (Weeks 16, 20, and 24) after visit 12. This data will not be included in the model but will be included in the summary table.

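### SAP 7.12.6.6 sends average-pain scores to the Week 16, 20 and 24 rows of the current-leg-pain summary, although current pain is recorded at those visits

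*SAP*

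**What the plan says.** SAP 7.12.6.6 concerns current pain in the affected leg. It states that current pain "is measured at every clinic visit and used for assessment of accuracy of pain reporting and monitoring of outlier values". Its response variable is the change in that score at Weeks 2, 4, 8 and 12, "with baseline NPRS score as the last score collected prior to the first injection on D1". The closing paragraph then turns to the later visits: "NPRS average scores are also collected at visits (Weeks 16, 20, and 24) after visit 12". It adds that these data stay out of the model but go into the summary table.

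Protocol 3.5.6.1 agrees on collection: current pain is "measured at every clinic visit and used for assessment of accuracy of pain reporting". The protocol synopsis, under the main efficacy parameters, lists current pain in the affected leg among the NPRS items taken at each study visit.

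On the other leg-pain items, Protocol 3.5.6.1 says that the diary runs to Week 12 and "thereafter, the NPRS will be collected at clinic visits only". SAP 7.12.6.5 says of worst pain after Week 12, "but this score is only collected once, that is, during the clinic visits".

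**The concern.** The section is about one item, and its rule for the later visits names another. Current pain is the intensity at the moment of asking. Average pain, as the diary defines it, looks back over 12 hours. If the rule is followed as written, the Week 2 to 12 rows of the table hold current pain and the Week 16 to 24 rows hold average pain. A step between Week 12 and Week 16 could then come from the change of item and be read as waning or lasting relief. The current-pain scores taken at those three visits would have no stated place in the table. If changes from baseline were also tabulated there, an average-pain score would have a current-pain baseline subtracted from it.

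**Working it through.** The plan gives no figure on this point, so the main check is a comparison of the SAP sections that add NPRS data from Weeks 16, 20 and 24 to a summary.

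| SAP section | Item in heading and model | Values to Week 12 | Baseline | Item named for Weeks 16, 20, 24 |
|---|---|---|---|---|
| 7.12.6.4 | average, affected leg | weekly mean | refers to 7.12.1, partly blacked out | average |
| 7.12.6.5 | worst, affected leg | weekly mean | mean of 5 to 7 days | worst, one clinic score |
| 7.12.6.6 | current, affected leg | clinic-visit score | last score before injection | **average** |
| 7.12.6.11 | average, low back | clinic-visit score | last score before injection | average |

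1. In three of the four sections the later item matches the heading and the model. Only 7.12.6.6 departs.
2. The sentence in 7.12.6.6 is word for word the one in 7.12.6.4 and 7.12.6.11, including its reference to visit 12 where Week 12 is evidently meant. The worst-pain section has its own wording. This points to text carried over from an average-pain section.
3. Missing data do not explain the switch. Three places in the documents have current pain recorded at clinic visits without an end at Week 12.
4. Blacked-out text does not explain it either, because the sentence is complete.

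A second, smaller check bears only on the optional footnote for 7.12.6.4 and 7.12.6.5. It asks how much noisier a change to one clinic score is than a change to a weekly diary mean. The documents give no SDs or correlations, so every input here is assumed.

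*First set of assumptions.* Let s be the SD of a single score, σ the SD of true change between subjects, and take 14 independent diary scores both per week and at baseline. The ratio of the SDs of change is √[(σ² + s²(1 + 1/14)) / (σ² + 2s²/14)].
- s = 1.0, σ = 2.5: √(7.321/6.393) = 1.07
- s = 1.2, σ = 2.0: √(5.543/4.206) = 1.15
- s = 1.5, σ = 2.0: √(6.411/4.321) = 1.22

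*Second set of assumptions.* Give a single entry unit variance, with within-week correlation ρ of 0.6 to 0.9, baseline-to-follow-up correlation λ of 0.3 to 0.5, and m = 10 to 14 baseline entries. With v(m) = ρ + (1 − ρ)/m, the ratio is √[(v(m) + 1 − 2λ) / (v(m) + v(14) − 2λ)].
- Smallest (ρ = 0.9, λ = 0.3, m = 10): √(1.310/1.217) = 1.04
- Largest (ρ = 0.6, λ = 0.5, m = 14): √(0.6286/0.2571) = 1.56

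If item and recall period are the same, averaging alone does not move the expected mean change. It affects spread only.

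Using a single-score baseline for these rows would not be a free remedy. Under the first set of assumptions it raises the variance of change from σ² + (15/14)s² to σ² + 2s². The SD rises by a further 6% (√(8.25/7.321)), 11% (√(6.88/5.543)) or 15% (√(8.50/6.411)). This is why the option below is to label the rows and show observed values, and not to redefine the baseline.

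**The case against.** The best reply is that nobody would be misled in practice. The heading, response variable and baseline of 7.12.6.6 all say current pain, and a programmer would probably use that item throughout. The sentence does not say that current-pain scores are dropped. SAP 7.1 says only that descriptive statistics for Weeks 16, 20 and 24 are added to the existing tables. The table list is blacked out, so the intended content cannot be seen.

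Much of this stands. The finished table may well be right, and carried-over wording is the likeliest cause. But a likely cause does not correct the rule. The sentence is an analysis instruction, it names the wrong item, and no other visible text overrides it.

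A reader might also infer a larger fault: that single clinic scores at Weeks 16 to 24 are set against a multi-day diary baseline for all leg-pain items. The documents do not support that.
- For current pain the baseline is itself a single score. The rule "Baseline NPRS score is the mean of at least 5 days and no more than 7 days of scores from the Screening visit" belongs to worst pain.
- For average leg pain, "Baseline and post-baseline values for this endpoint is obtained as discussed in" Section 7.12.1, where text is blacked out.
- No NPRS section says that the Week 16 to 24 rows are changes from baseline.
- The SAP discloses the single clinic score for worst pain and keeps it out of the model. At any one visit all groups are measured in the same way.

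**Conclusion.** The point holds for 7.12.6.6. As written, all three time points after Week 12 in the current-leg-pain summary carry average pain. This rests on the statements that current pain is taken at every clinic visit; the schedule of assessments, which could confirm them, is blacked out.

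The consequence is small. Only descriptive rows are touched, and they enter with the full analysis after Week 24. The primary endpoint, the key secondary endpoint and the modelled Week 2 to 12 results are unaffected.

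It would go too far to call these rows the trial's only long-term pain figures. Low back NPRS is summarized at Weeks 16, 20 and 24 on a consistent clinic-score basis (7.12.6.11). PainDETECT and BPI-SF are summarized at Week 24 (7.12.6.8 and 7.12.6.9). Nor is it true that no model reaches beyond Week 12, because time to repeat injection has a Cox model with censoring at 20 weeks (7.12.6.2).

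The change from weekly diary means to single clinic scores in 7.12.6.4 and 7.12.6.5 is a matter of labelling, not an error. The spread ratios of 1.04 to 1.56 illustrate why a label helps; they are not estimates for this trial.

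**What to change.** In the last paragraph of SAP 7.12.6.6, name *NPRS current pain scores in the affected leg* instead of average scores for Weeks 16, 20 and 24. Check that the table shell and program draw the same item. The protocol needs no change.

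Optional: in 7.12.6.4 and 7.12.6.5, footnote the Week 16, 20 and 24 rows as single clinic scores, not weekly diary means, and state that they are shown as observed values.

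The cost is one phrase of SAP text and, if the option is taken, two footnotes. No new data and no new model are needed.

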#### **7.12.6.7 The mean change from Baseline (D1) in the ODI total score to Week 12.**

The treatment group categories will be: SP-102/SP-102, PBO/SP-102, SP-102/none, PBO/none. As part of this analysis, comparisons will test the mean LS mean differences between the following groups:

- SP-102/none vs. PBO/none

- SP-102/SP-102 vs. PBO/none
- SP-102/none vs. PBO/SP-102
- SP-102/SP-102 vs. PBO/SP-102

An MMRM analysis will be applied using the four treatment groups to analyze change from baseline in ODI through Week 12 (Weeks 4 and 12). ODI at Week 24 will be summarized. The change from baseline at Weeks 4 and 12 will be the response variable with fixed effects for treatment, Week, site, Pain Catastrophizing Scale group (<30 or ≥30), baseline ODI, and treatment-by-week interaction. The following SAS code will be used for this analysis;

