
Planned Sample Size:
	
Approximately 400 subjects will be randomized in this study. The sample size goal of this study is for 332 subjects to complete W4.

Key Subject Selection Criteria:
	
Inclusion Criteria: Screening Visit Inclusion Criteria (D-22 to D-8)
 
 1. Able and willing to read, write, and understand the English language and provide English-language written informed consent prior to beginning any study procedures. 2. Age 18 to 70 years (inclusive) at the Screening Visit. 3. A diagnosis of lumbosacral radicular pain at the Screening Visit. 
[REDACTED]

	
 [REDACTED] [REDACTED] [REDACTED] [REDACTED] [REDACTED] [REDACTED] [REDACTED] [REDACTED] [REDACTED] 
10. If sexually active and a female of childbearing potential or a male capable of bearing a child, agrees to use an effective method of birth control during the study. [REDACTED]
 
 [REDACTED] [REDACTED] [REDACTED] [REDACTED] [REDACTED] 
12. Reviewed all study-specific educational materials and has, in the opinion of the Investigator, the cognitive abilities to understand and appropriately complete all study-mandated procedures.
 
 [REDACTED] [REDACTED]
--	--

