[REDACTED] Eligible subjects will then be randomly assigned (in a 1:1 ratio) on D1 to receive a single dose of an SP-102 TF, or placebo [REDACTED] in the vicinity of the epidural space or [REDACTED] under fluoroscopic guidance (for instructions on study drug injection see [Appendix D](#)). This first injection is referred to as the “index injection”. An appropriately trained physician, hereafter called the Injection Physician, administering the DB investigational product (IP) and other assisting staff (eg, nurse) will, therefore, not be blinded to the treatment assignment, while the rest of study staff involved in assessments and collection of data will remain blinded. Procedures will be in place at each site to ensure blinding, minimizing personnel involved with injection, and guarantee sequestration of imaging data acquired at the time of injection.

Fluoroscopic imaging guidance is required by this protocol to ensure proper placement of the injection needle (see instructions in [Appendix D](#)). Long-term persistent AEs are rarely seen with fluoroscopically-guided lumbosacral TF injections, however immediate and delayed AEs may include vasovagal episodes, procedure interruption from intravascular flow, pain exacerbation, injection site soreness, headache, and insomnia ([Plastaras-2015](#)). Avoidance of risk of procedural AEs in the placebo group by implementing an [REDACTED]

[REDACTED] is consistent with ethical considerations and use of [REDACTED] in interventional/surgical clinical trials (Wartolowska-2014). In addition to safety considerations and lowering the risk of procedural complication in the control group, the choice of an [REDACTED]

The choice of the TF injection approach with direct deposition of drug near the ventral epidural space at the affected level is selected based on published reviews documenting better effectiveness as compared to other approaches. For lumbar disc herniation with unilateral symptoms, the evidence for analgesic effect and ability to prevent surgery is greater for TF epidural injections as compared to caudal or interlaminar approaches (Manchikanti-2012; Cohen-2013).

[figure not shown]

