## 7.12 Efficacy Analyses

All statistical tests will be performed using a two-tailed 5% overall significance level, unless otherwise stated. All comparisons between treatments will be reported with 95% confidence intervals (CI) for the difference. Pain profiles through the first four weeks will be presented by the treatment received for the first injection (SP-102, Placebo). Moreover, pain profiles through 12 weeks will be presented by treatment received for second injection (SP-102/SP-102, PBO/SP-102, SP-102/none, PBO/none). Also, the ‘site’ indicated in this section refers to the final pooled sites as described in [Section 7.2.10](#).

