### 7.12.2 Primary Efficacy Analysis

The primary comparison will use a linear contrast of the least squares (LS) means comparing the mean weekly mean scores up to Week 4 (average of Weeks 1, 2, 3, and 4 change from baseline LS means estimated from the model).

For each type of pain score collected, NPRS scores will be summarized on a weekly basis (Weeks 1, 2, 3, and 4). The LS means, its corresponding standard errors and 95% CI will be presented for all four weeks. The same will be presented for the mean LS mean corresponding to the mean weekly mean scores across all four weeks. The estimate of the LS mean treatment difference, its standard error, and 95% CI will be presented for the average LS mean across all four visits.

The SAS code anticipated to be used for the analysis of the primary efficacy endpoint is as follows:

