**7.12.6.8 The mean change in PainDETECT from Baseline (D1) to Week 4 and Week 12.**

PainDETECT is a 7-question validated tool to determine the prevalence of neuropathic pain in individuals with lower back pain. The 7 responses, with possible values of never (0), hardly noticed (1), slightly (2), moderately (3), strongly (4), and very strong (5), are summed for a possible score ranging from 0-35. In addition to the 7 questions, subjects note the course of pain (Persistent pain with slight fluctuations; Persistent pain with pain attacks, Pain attacks without pain between them; Pain attacks with pain between them) with 0, -1, 1, and 1 score assignments respectively, and whether the pain radiates to other regions of the body or not which adds 2 to the total score for a “yes” response and 0 for a missing or “no” response. Hence, the total overall scale score will range from 0 to 38. Baseline PainDETECT total score is defined as the last score collected prior to the first injection on D1. Since this endpoint is summing the responses to get the total score, if a subject is missing a question aside from the question on whether the pain radiates to other regions of the body or not, the total score will not be calculated for that subject. PainDETECT will be collected at Baseline (D1), Week 4, and Week 12.

PainDETECT at Week 4 will be analyzed using an ANCOVA model with change from baseline at Week 4 as the response variable with fixed effects for treatment (two groups: SP102 or placebo), site, Pain Catastrophizing Scale group (<30 or ≥30), and baseline PainDETECT total score.

Change from baseline to Week 12 will also be analyzed using an MMRM analysis with change from baseline to Week 12 (Weeks 4 and 12) as the response variable, with fixed effects for treatment (SP-102/SP-102, PBO/SP-102, SP-102/none, PBO/none) week, site, Pain Catastrophizing Scale group ( $<30$  or  $\geq 30$ ), baseline score, and treatment-by-week interaction. As part of this analysis, comparisons will test the mean LS mean differences between the following groups:

- SP-102/none vs. PBO/none
- SP-102/SP-102 vs. PBO/none
- SP-102/none vs. PBO/SP-102
- SP-102/SP-102 vs. PBO/SP-102

Pain*DETECT* will be summarized for Week 24 by treatment (four groups).

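### The Week 12 ODI test names no week and, on the SAP's only visible definition of its contrast, averages Weeks 4 and 12; PainDETECT and BPI-SF share the wording

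*SAP*

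**What the plan says.** SAP 7.12.2 sets the primary comparison as the average of the Week 1 to 4 LS means from the model. It then uses the term in question for that average: "The same will be presented for the mean LS mean corresponding to the mean weekly mean scores across all four weeks". No other definition of the term is visible.

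SAP 7.12.6.7 covers the change in ODI to Week 12. Its model has two visits: "The change from baseline at Weeks 4 and 12 will be the response variable". It includes a treatment-by-week interaction and uses the four injection-sequence groups. For the tests, "comparisons will test the mean LS mean differences between the following groups", followed by four pairs of groups. No week is attached.

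SAP 7.12.6.8 (PainDETECT) follows the same pattern: a Week 4 ANCOVA in the two arms, then a four-group model of Weeks 4 and 12 in which "comparisons will test the mean LS mean differences between the following" pairs of groups. SAP 7.12.6.9 (BPI-SF) does likewise but calls the comparisons post-hoc. Week 4 ODI is the key secondary endpoint and has its own two-arm ANCOVA in SAP 7.12.5.

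For PGIC and CGIC (7.12.6.1 and 7.12.6.12), by contrast, the SAP promises an odds ratio at each named week.

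**The concern.** An endpoint named for Week 12 should be decided by the difference at Week 12. If the term keeps its 7.12.2 meaning, the ODI contrast gives equal weight to Week 4 and Week 12. Week 4 is the visit at which the repeat-injection window opens, and its ODI data are already used for the key secondary endpoint, there by randomised arm.

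Two errors of interpretation follow. An effect that has gone by Week 12 can still give a significant result under a Week 12 label. An effect present only at Week 12 is halved in the contrast and may be missed. What is at stake is any statement about durability at Week 12. The primary and key secondary analyses are not touched.

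**Working it through.** **Figures in the plan.** The Protocol synopsis says "Approximately 400 subjects will be randomized in this study" and "The sample size goal of this study is for 332 subjects to complete W4". These imply attrition of 1 - 332/400 = 17%, and 332/0.83 = 400, so the two figures fit together. The effect size, SD and power behind them are blacked out in the public copy, so the sample size cannot be rebuilt. The documents give no power or error rate for the Week 12 comparisons.

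**Inputs.** From SAP 7.12: "All statistical tests will be performed using a two-tailed 5% overall significance level, unless otherwise stated". From SAP 7.12.6.7: Weeks 4 and 12 in the model. Assumed, because no values are visible: SD of ODI change 12 to 18, equal at both visits; correlation between visits (rho) 0.5 to 0.7; two compared groups of 100 and 70; normal approximation.

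**Formulas.** With d4 and d12 the true differences at Weeks 4 and 12:

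- Averaged contrast = (d4 + d12)/2, with SE = SD × sqrt((1 + rho)/2) × sqrt(1/100 + 1/70).
- Week 12 contrast = d12, with SE = SD × sqrt(1/100 + 1/70).
- sqrt(1/100 + 1/70) = 0.1558.
- Chance of p < 0.05 = Phi(|contrast|/SE - 1.96) + Phi(-|contrast|/SE - 1.96).

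**Difference at Week 4 only (d4 = -6, d12 = 0).** The averaged contrast is -3.

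| SD | rho | SE of average | 3/SE | Average significant | Week 12 contrast significant |
|---|---|---|---|---|---|
| 12 | 0.5 | 12 × 0.8660 × 0.1558 = 1.62 | 1.85 | 45.7% | 5% |
| 15 | 0.5 | 15 × 0.8660 × 0.1558 = 2.02 | 1.48 | 31.7% | 5% |
| 18 | 0.7 | 18 × 0.9220 × 0.1558 = 2.59 | 1.16 | 21.3% | 5% |

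With d4 = -8 the range is 34.0% to 69.5%.

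**Difference at Week 12 only (d4 = 0, d12 = -6).** The average is again -3, so its power is the same 21% to 46%. The Week 12 contrast has SE 12 × 0.1558 = 1.87 to 18 × 0.1558 = 2.81, and power 89% to 57%.

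**Second set of assumptions.** Take 332/4 = 83 per group, rho 0.5, and a Week 4 difference of 0.5 SD with none at Week 12. The average is 0.25 SD, its SE is 0.8660 × sqrt(2/83) = 0.134 SD, and the chance of significance is 46%. A simulation of 20,000 trials gave 45.8% for the average and 4.9% for the Week 12 contrast. With 0.5 SD at Week 12 only, power is 46% for the average and 90% for the Week 12 contrast.

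**Price of the Week 12 contrast.** The ratio of standard errors is 1/sqrt((1 + rho)/2): 1.15 at rho 0.5 and 1.08 at rho 0.7.

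**The case against.** The strongest reply is that the deciding text cannot be seen. SAP 7.12.6.7 ends by announcing SAS code that is not in the public copy, and the ordered list of tests in 7.12.6.19 is blacked out. The code may request week-specific estimates, and these four-group comparisons may not be in the ordered sequence. The term is defined for the four-week primary model and is not restated for the 12-week models. In 7.12.6.5, 7.12.6.17 and 7.12.6.18 an overall average is mentioned for the first four weeks but not for the 12-week analysis, which hints at by-week results there. All of this stands, and it limits the point to the visible wording. It does not remove it: even if the term is loose wording, the tested week is still unnamed.

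Four stronger inferences are tempting, and the documents do not support them.

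- *The Week 12 test has a type I error of 21% to 46%.* In the first scenario the averaged contrast truly equals -3, so these percentages are power for a different estimand under assumed inputs.
- *The pain endpoints are tested at the wrong time.* SAP 4.3 lists average, worst, current and low-back pain at Weeks 2, 4, 8 and 12, so an average over those weeks stays within the named weeks.
- *A short-lived effect will be reported as a Week 12 effect.* No visible text says so. SAP 7.12.5 has ODI and its change summarised by visit and group, so a null Week 12 result could be seen beside the test.
- *A Week 12 contrast would give a clean durability result.* The four groups are formed after randomisation, by receipt of a repeat injection that depends partly on leg pain. The calculation above treats them as simple independent groups and does not address that selection.

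**Conclusion.** The point holds for the Week 12 ODI test and, with the same wording, for the Week 12 models of PainDETECT and BPI-SF; the BPI-SF comparisons are labelled post-hoc. Followed as written, with the only visible definition of the term, the ODI contrast is the average of Weeks 4 and 12 and does not answer the question that the endpoint asks.

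The direction does not depend on the assumptions: when Week 12 is null, any non-zero Week 4 difference pushes the chance of significance above 5%. The size does depend on them. The range of about 21% to 46% rests on assumed SDs, correlations, group sizes and a Week 4 difference of -6.

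For the pain scores, only a labelling point remains. This deserves correction before unblinding but does not bear on the primary or key secondary result.

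**What to change.** In SAP 7.12.6.7, 7.12.6.8 and 7.12.6.9, replace the mean LS mean differences by *the LS mean difference at Week 12, from the treatment-by-week term*, and state that this is the deciding contrast for the Week 12 endpoint. Label any average over Weeks 4 and 12 as a separate summary. Check that the SAS code matches.

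For the pain scores (7.12.6.4 to 7.12.6.6, 7.12.6.11, 7.12.6.17 and 7.12.6.18), state that the average covers Weeks 2, 4, 8 and 12, and do not report it as a Week 8 or Week 12 effect. Show by-week differences as descriptive only. Testing four pairs at four weeks would mean 16 tests per endpoint instead of 4.

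The cost is a wording change and one estimate line in each of the ODI, PainDETECT and BPI-SF models. The standard error in these two-visit models rises by about 8% to 15% at correlations of 0.7 to 0.5. The number of tests for these endpoints does not change. The separate problem of groups formed after randomisation remains and needs its own answer.
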